11.0 EVALUATION DURING TREATMENT/INTERVENTION

11.1 Adverse Event (AE) Monitoring

The investigator or qualified designee will assess each participant to evaluate for potential new or worsening AEs as specified in the Trial Flow Chart and more frequently if clinically indicated. Adverse experiences will be graded and recorded throughout the study and during the follow-up period according to NCI CTCAE Version 5.0 (see Appendix 2). Toxicities will be characterized in terms regarding seriousness, causality, toxicity grading, and action taken with regard to trial treatment.

Memorial Sloan Kettering Cancer Center IRB Number: 20-481 A(11)

Approval date: 11-Jun-2024 Page | **39**

All assessments will be performed on the day of the scheduled visit date unless a time window is specified. Assessments scheduled on the days of study treatment should be performed before the infusion of study drug(s) unless otherwise noted. If the timing of a study visit coincides with a holiday, weekend, or other administrative disruption that precludes the visit, the visit should be scheduled on the nearest following feasible date, with subsequent visits rescheduled accordingly.

Table 9. Schema for treatment and evaluations.

Trial Period:	Screening Phase		Trea	ıtmen	ıt Cy	cles	(21 D	ay C	ycles)	Pembro Q6 Wk		End of Treatment	Post-Treatment	
Treatment Cycle/Title:	Pre- screening (Visit 1)	1	2	3	4	5	6	7	8	9	Even Cycles (ex. 10, 12, 14 etc.)	Odd Cycles (ex. 11, 13, 15, etc.)	Discontinua tion	Safety Follow-up (in clinic)	Survival Follow- Up (Clinic or phone)
Scheduling Window (Days):	-28		± 3	± 3	± 3	At time of Discontinua tion	30 days and 60 days post discontinuation	Every 12 weeks for 5 years							
Administrative Procedures															
Informed Consent	Х														
Inclusion/Exclusion Criteria	Х														
Demographics and Medical History	Х														
Prior and Concomitant Medication Review	х	х	х	Х	х	х	х	х	х	Х	Х	X**	х	Х	Х
Pembrolizumab** Administration		х	х	Х	Х	х	х	х	х	х	Х	X**			
Survival Status	Х	Х	Х	Х	Х	Х	Х	Х	Х	Х	Х	X**	Х	Х	Х
Clinical Procedures/A	Clinical Procedures/Assessments														
Review Adverse Events		х	Х	X	Х	Х	Х	Х	Х	Х	X	X**	Х	Х	×
Full Physical Examination	Х	х	Х	х	Х	Х	х	х	х	х	х		Х		

Trial Period:	Screening Phase		Trea	ıtmer	nt Cy	cles	(21 C	ay C	ycles)	Pembro Q6 Wk End of Treatment			Post-Treatment	
Treatment Cycle/Title:	Pre- screening (Visit 1)	1	2	3	4	5	6	7	8	9	Even Cycles (ex. 10, 12, 14 etc.)	Odd Cycles (ex. 11, 13, 15, etc.)	Discontinua tion	Safety Follow-up (in clinic)	Survival Follow- Up (Clinic or phone)
Scheduling Window (Days):	-28		± 3	± 3	±3	At time of Discontinua tion	30 days and 60 days post discontinuation	Every 12 weeks for 5 years							
Directed Physical Examination	Х	x	х	х	Х	х	x	x	x	х	х		Х		
Vital Signs and Weight	Х	х	х	Х	х	х	х	х	х	Х	Х		Х	Х	
ECOG Performance Status	Х	х	х	Х	Х	х	х	Х	х	х	х		Х		
Laboratory Procedure	s/Assessment	s: an	alysi	is per	form	ned b	y LO	CAL	labor	atory					
Pregnancy Test – Urine or Serum □- HCG	Х	х													
PT/INR and aPTT	Х												Х		
CBC with Differential	Х	Х	х	Х	х	х	х	х	Х	Х	Х		Х		
Comprehensive Serum Chemistry Panel	Х	х	х	Х	х	х	х	х	х	Х	Х		х		
CA 19-9, CEA	Х	Х	Х	Х	Х	Х	Х	Х	Х	Х	Х		Х		
HBsAg, IgG anti- HBs, Anti-HCV, HIV screen	х														

Trial Period:	Screening Phase		Trea	itmen	ıt Cy	cles	(21 D	ay C	ycles)	Pembro Q6 Wk		End of Treatment	Post-Treatment	
Treatment Cycle/Title:	Pre- screening (Visit 1)	1	2	3	4	5	6	7	8	9	Even Cycles (ex. 10, 12, 14 etc.)	Odd Cycles (ex. 11, 13, 15, etc.)	Discontinua tion	Safety Follow-up (in clinic)	Survival Follow- Up (Clinic or phone)
Scheduling Window (Days):	-28		± 3	± 3	± 3	At time of Discontinua tion	30 days and 60 days post discontinuation	Every 12 weeks for 5 years							
Urinalysis	Х			Х			Х			Х	Х				
FT3, FT4 and TSH	Х			Х			Х			Х	Х				
EKG	Х			Х			Х			Х	Х				
Efficacy Measurement	s														
Tumor Imaging*	Х				Х			Х			>	(*	Х		
Tumor Biopsies/Archi	Tumor Biopsies/Archival Tissue Collection/Correlative Studies Blood														
Biopsy ^{1, 2, 3}	Х			Х									Х		
Correlative Studies Blood Collection ⁴	Х			Х			Х				>	⟨⁴	Х		
Blood draw to generate plasma for cell free (cf)DNA analysis ⁵	Х			Х			Х				>	〈 5	Х		

Trial Period:	Screening Phase	Treatment Cycles (21 Day Cycles)									Pembro	Q6 Wk	End of Treatment	Post-Treatment	
Treatment Cycle/Title:	Pre- screening (Visit 1)	1	2	3	4	5	6	7	8	9	Even Cycles (ex. 10, 12, 14 etc.)	Odd Cycles (ex. 11, 13, 15, etc.)	Discontinua tion	Safety Follow-up (in clinic)	Survival Follow- Up (Clinic or phone)
Scheduling Window (Days):	-28		± 3	± 3	±3	At time of Discontinua tion	30 days and 60 days post discontinuation	Every 12 weeks for 5 years							

- * Computed Tomography (CT) Chest/abdomen/pelvis with oral and IV contrast or CT chest without contrast AND Magnetic Resonance Imaging (MRI) abdomen/pelvis with contrast if IV contrast/iodine allergy. Imaging frequency every 9-weeks from treatment initiation until Cycle 10, then every 12-week thereafter. If a participant has remained on study for greater than 2 years, imaging can be transitioned to every 3-6 months per MD discretion. Imaging evaluation must be done within +/- 7 days of the planned schedule. Per the treating MD's discretion, imaging can be done before the ontreatment biopsy.
- ** Pembrolizumab 400 mg every 6 weeks will be started on Cycle 10 Day 1. Patients will need to come to clinic during odd cycles post Cycle 10, only if clinically indicated. Per treating investigator's discretion, patients may remain at Pembrolizumab 200 mg IV every 3 weeks after the first 9 cycles. Additionally, to accommodate patients traveling far distances, if, per treating investigator, after the first or second imaging, there are no toxicities, patient's dosing of Pembrolizumab may change to 400 mg IV every 6 weeks. Telehealth visits are allowed.
- 1. **Pre-treatment (baseline) Tumor Tissue:** All patients must submit FFPE tumor tissue (#1 core), fresh tissue (75% of #2 core, #3, and #4 core for scRNAseq and only 25% of #2 core for organoid), and flash frozen tumor tissue (#5, 6, and any extra cores for snRNAseq, whole genome sequencing, and MIBI if possible) as per detailed biomarker management plan (BMP). The goal is to obtain 4-6 cores where clinically safe and feasible at baseline within 2-3 weeks before starting the treatment. In patients participating with major PR or CR may not have enough disease at baseline for multiple biopsies.
- 2. **Tumor Biopsy during Treatment (on-treatment) Period:** Repeat biopsy for on-treatment tumor tissue is requested for study purpose for patients between the 6th to 9th week (+/- 1 week) before the first repeat imaging in the 9th week. Per the treating MD's discretion, imaging can be done before the on-treatment biopsy.
- 3. **Tumor Biopsy at End of Treatment (on progression):** Every effort should be made to obtain EOT (+/- 28 days) biopsies in cases of RECIST v1.1 confirmed disease progression if a patient discontinues study treatment due to disease progression, except in instances where the procedure, as performed in the clinical research setting, poses an unacceptable risk to the patient.
- 4. **Blood draw to analyze circulating immune cell profiling:** 4 x 10ml Green-top sodium heparin tubes at 6 time points will be collected: #1 at baseline lab, #2 +/- 7 days from on-treatment biopsy date (for patients who are unable to get an on-treatment biopsy, this timepoint can be collected at C3 or C4), #3 with C6D1 lab, #4 with C12D1 lab, #5 with C18D1 lab, and #6 with EOT (+/-21 days).
- 5. Blood draw to generate plasma for cfDNA: TOPCOAT-POLAR will handle for MSK ACCESS #1-#6 time points for All Cohorts, we will bank them as cfDNA.

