4.2 Intervention

A variety of factors that could potentially predict clinical response to the POLAR regimen will be investigated in peripheral blood and in tumor specimens taken from all participants pretreatment (screening phase), on-treatment, and at the time of disease progression, as outlined in the Treatment and Biospecimen Schema in Figure 1. Data from these investigations will be evaluated for associations with treatment response to POLAR, survival (OS, PFS), and safety (AE).

Research Tissue Collection

All participants will undergo a pre-treatment research biopsy and cfDNA at baseline and during treatment. (Figure 1.) All patients will receive the combination of pembrolizumab 200 mg IV

6

POLAR: a phase 2 trial for pembrolizumab and olaparib maintenance for metastatic PDAC and HRD and/or Exceptional Response to Platinum – Ver. 5/3/2020

every 3 week and olaparib 300 mg twice day orally daily (POLAR) as maintenance therapy. After the first 6 months (9 cycles), on C10D1 Pembrolizumab 400 mg IV every 6 week plus olaparib 300 mg twice a day orally will be continued. At the discretion of the treating investigator, Pembrolizumab 400 mg IV every 6 weeks may begin earlier or Pembrolizumab 200 mg IV every 3 weeks may be continued after C10D1. An on-treatment biopsy (on the 6th- 9th week) and post-progression (before initiation of further therapy) will be obtained where feasible. Biopsies are mandated by protocol baseline and on treatment and at the time of progression except in the setting that there is no disease site that can be safely assessed for biopsy or other clinically relevant safety reason. If tissue acquisition is limited due to availability, available tissues will be prioritized in the following order.

- 1) FFPE (WES, multiplex immunohistochemistry)
- 2) Fresh tissue for single cell analysis with 10-20% cut for organoid culture
- 3) Fresh tissue for single cell analysis
- 4) Fresh frozen for archival

Patients will be presented at multidisciplinary tumor board for discussion related to biopsy safety and site choice were needed. Selected patients with disconcordant and heterogenous response can include up to three different sites for tissue sampling as long as deemed safe.

Research Blood Collection

Peripheral blood mononuclear cells, buffy coat, and plasma will be collected. Circulating tumor DNA on these patients identified as responders and resistant patients will be compared.

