10.0 TREATMENT/INTERVENTION PLAN

10.1 Administration

Within 4 weeks of screening date, eligible patients will receive combination pembrolizumab and olaparib as maintenance therapy until clinical or radiographic progression or discontinuation due to -limiting toxicity. If a patient requires discontinuation of either olaparib or pembrolizumab for reasons of toxicity and if in the opinion of the treating MD the patient is continuing to derive benefit, the patient is able to continue on study. Additionally, in the absence of unacceptable toxicity, participants who meet criteria for disease progression per RECIST 1.1 while receiving treatment will be permitted to continue treatment, if in the opinion of the treating MD the patient is continuing to derive benefit from the treatment. iRECIST will be used to evaluate the objective response rate and the co-primary endpoint of overall response rate will be assessed by RECIST v1.1. (Section 12.0 CRITERIA FOR REMOVAL FROM STUDY).

The POLAR treatment will be administered to subjects as outlined in Figure 1 - Schematic treatment and biospecimen collection schedule. Approximately within 4 weeks of screen visit, patient will get baseline biopsy and will start the first dose pembrolizumab 200 mg IV every 3 weeks and olaparib 300 mg twice daily orally. After the first 6 months (9 cycles), on C10D1 Pembrolizumab 400 mg IV every 6 week plus olaparib 300 mg twice a day orally will be continued. Per treating investigator's discretion, patients may remain at Pembrolizumab 200 mg IV every 3 weeks after the first 9 cycles. Additionally, to accomodate patients traveling far distances, if, per treating investigator, after the first or second imaging, there are no toxicities, patient's dosing of Pembrolizumab may change to 400 mg IV every 6 weeks. All cycles will be 21 days (3 weeks) in length. Subjects will be monitored for toxicity every three weeks for the first 9 cycles, and every six weeks thereafter, unless clinically indicated to be monitored every 3 weeks.

Table 2. Trial treatment (POLAR)

Drug	Dose	Dose Frequency	Route of Administration	Treatment Period	Use
Pembrolizumab	200 mg	Q3W	IV infusion	Day 1 of each 3- week cycle for cycle 1-9	experimental
Pembrolizumab	400mg	Q6W	IV infusion	Day 1 of every even cycle beginning with Cycle 10	experimental
Olaparib	300 mg (two 150 mg)	BID	Orally	Daily continuously	experimental

The following parameters must be acceptable prior to initiation of protocol treatment:

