10.2 Timing of Dose Administration

Trial treatment should be administered on Day 1 of each cycle after all procedures or assessments have been completed as detailed on the Trial Flow Chart (Section 6.0). Trial treatment may be administered up to 3 days before or after the scheduled Day 1 of each cycle due to administrative reasons. On the day of the treatment, participants can receive oral olaparib AM dose at the clinic visit followed by pembrolizumab.

All trial treatments will be administered on an outpatient basis.

Pembrolizumab will be infused per MSK guidelines. Pembrolizumab 200 mg will be administered as a 30-minute IV infusion every 3 week. After the first 6 months (9 cycles), on C10D1 Pembrolizumab 400 mg IV every 6 week plus olaparib 300 mg twice a day orally will be continued. Pembrolizumab 200 mg IV every 3 weeks may continue after Cycle 9, and Pembrolizumab 400 mg IV every 6 weeks may begin earlier than Cycle 9 per treating physician's discretion. Given the variability of infusion pumps a window of -5 minutes and +10 minutes is permitted (i.e., infusion time is 30 minutes: -5 min/+10 min).

8

POLAR: a phase 2 trial for pembrolizumab and olaparib maintenance for metastatic PDAC and HRD and/or Exceptional Response to Platinum – Ver. 5/3/2020

10.3 Dose Modification and Toxicity Management for Immune-Related AEs Associated with Pembrolizumab

AEs associated with pembrolizumab exposure may represent an immunologic etiology. These immune-related AEs (irAEs) may occur shortly after the first dose or several months after the last dose of pembrolizumab treatment and may affect more than on body system simultaneously. Therefore, early recognition and initiation of treatment is critical to reduce complications. Based on existing clinical study data, most irAEs were reversible and could be managed with interruptions of pembrolizumab, administration of corticosteroids and/or other supportive care. For suspected irAEs, ensure adequate evaluation to confirm etiology or exclude other causes. Additional procedures or tests such as bronchoscopy, endoscopy, skin biopsy may be included as part of the evaluation. Based on the severity of irAEs, withhold or permanently discontinue pembrolizumab and administer corticosteroids. Dose modification and toxicity management guidelines for irAEs associated with pembrolizumab are provided in Table 3.

Table 3 Dose modification and toxicity management guidelines for immune-related AEs associated with pembrolizumab

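### Patients kept on 3-weekly pembrolizumab after Cycle 9 are infused at odd cycles for which Table 9 schedules no CBC or chemistry

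*Protocol*

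**What the plan says.** **The 3-weekly option.** The default from C10 is pembrolizumab 400 mg every 6 weeks, given on even cycles (Protocol, Table 2). The investigator may instead leave a patient on the earlier regimen. The Table 9 footnote in Section 11.1 says "patients may remain at Pembrolizumab 200 mg IV every 3 weeks after the first 9 cycles". Section 10.2 says "Pembrolizumab 200 mg IV every 3 weeks may continue after Cycle 9", and Section 4.2 says "Pembrolizumab 200 mg IV every 3 weeks may be continued after C10D1". Sections 1.0, 3.3, 4.1 and 10.1 give the same option.

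**The visit schedule.** From Cycle 10, Table 9 has one pair of treatment columns, even and odd cycles, under a header naming six-weekly pembrolizumab. In the odd-cycle column, the row "Pembrolizumab Administration" carries X**, as do concomitant medication review, survival status and adverse event review. The row "Comprehensive Serum Chemistry Panel" is blank there, and so is the CBC row. Footnote ** adds: "Patients will need to come to clinic during odd cycles post Cycle 10, only if clinically indicated".

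**Monitoring and pre-dose checks.** Section 10.1 sets toxicity monitoring at every three weeks for nine cycles "and every six weeks thereafter, unless clinically indicated to be monitored every 3 weeks". Section 11.1 says: "Assessments scheduled on the days of study treatment should be performed before the infusion of study drug(s) unless otherwise noted". Section 10.2 likewise ties dosing to completion of what the flow chart lists. The numeric laboratory limits in Section 10.1 apply before treatment starts, not before each later dose.

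**The concern.** Table 3 tells the investigator to withhold pembrolizumab for an immune-related Grade 2 rise in AST/ALT, bilirubin or creatinine, and to stop it permanently at Grade 3 or 4. These rules can be applied only if there is a laboratory value. Through Cycle 9, and on the default six-weekly regimen, chemistry is scheduled at every infusion. For a patient kept on 3-weekly dosing it is scheduled at every second infusion only.

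Adverse event review at the odd cycle does not fill this gap. An enzyme or creatinine rise without symptoms is not found by questioning, and gives no clinical reason to order an unscheduled test. What is lost is the scheduled opportunity to hold the second 200 mg of each six-week interval.

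**Working it through.** The protocol states no figure to reproduce. The check is a count of Table 9 cells and calendar arithmetic.

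**Inputs.** Cycle length 21 days (Section 10.1). Dosing window plus or minus 3 days (Section 10.2). CBC and chemistry marked at screening, Cycles 1 to 9, even cycles from 10, and discontinuation (Table 9). Assumption: even-cycle bloods are drawn on the dosing day.

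**Calendar.** Day 1 of cycle k is day 21 × (k − 1) + 1.

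| Visit | Day | Chemistry scheduled | 3-weekly patient | Default patient |
|---|---|---|---|---|
| C10D1 | 190 | yes | 200 mg | 400 mg |
| C11D1 | 211 | no | 200 mg | none |
| C12D1 | 232 | yes | 200 mg | 400 mg |

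**Age of the last scheduled chemistry at C11, C13 and so on.** 211 − 190 = 21 days. If both visits use the window in opposite directions, the range is 21 − 6 = 15 to 21 + 6 = 27 days.

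**Share of drug without same-day scheduled chemistry.** 3-weekly after Cycle 9: 200 / (200 + 200) = 50%. Default regimen: 0 / 400 = 0%. Cycles 1 to 9: 0%.

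**Drug between scheduled labs.** 200 + 200 = 400 mg per 42 days on 3-weekly dosing, and 400 mg per 42 days on the default. These are equal.

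**First infusion affected.** C11D1 is 210 days after the start of treatment: 210 / 7 = 30 weeks, or 210 / 30.44 = 6.9 months. Section 1.0 expects an average of 4 months on treatment. Against that, Section 14.0 plans Cohort A around a 6-month PFS rate between 53% (null) and 77% (target), and the Table 9 footnote provides for patients on study beyond 2 years. Treatment past Cycle 10 is therefore foreseen.

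**Could another rule supply the labs?** Sections 10.2 and 11.1 require before dosing only what the chart schedules, and the chart schedules no labs at odd cycles from C11. Section 10.1 sets the frequency by cycle number, not by regimen. No other column of Table 9 covers a 3-weekly patient after Cycle 9.

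**Is the blank a PDF artefact?** Unlikely. The odd-cycle cell is empty in the same way for physical examination, vital signs, ECOG, CBC, chemistry and tumour markers, while four other rows keep their X**.

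**After the change proposed below.** The lab interval for a 3-weekly patient falls from 42 to 21 days, and the age of the values at C11, C13 and so on falls from 21 days to 0.

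**The case against.** The best counter-argument is about scope. The even and odd columns are headed for six-weekly pembrolizumab, and the sentence on odd-cycle attendance comes straight after the statement that 400 mg every 6 weeks starts at C10. A patient with a 3-weekly infusion has to attend at odd cycles, so that sentence was probably written for others. On this view, someone who stays on 200 mg simply continues the Cycle 2 to 9 pattern, with bloods every time.

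That may well be the intent, but the text does not say it. If the columns are for six-weekly patients only, Table 9 has no on-treatment schedule for 3-weekly patients after Cycle 9. The X** for pembrolizumab at odd cycles also has no use for a default patient, who is dosed on even cycles.

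Other points against the concern stand and limit it:

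- Unscheduled visits and 3-weekly monitoring are allowed when clinically indicated. Table 3 also suggests liver tests weekly or more often once a value is abnormal. The gap is confined to a new, silent rise within about three weeks of an acceptable result.
- Section 10.2 refers infusion to institutional guidelines. Whether these call for pre-infusion bloods cannot be judged from the protocol.
- A raised value at C11 would not by itself oblige the investigator to stop. Section 10.4 applies the guidance to events judged related to pembrolizumab, and Section 10.3 lets a patient with Grade 3 liver tests not attributed to the drug continue.

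A reader might also infer that 3-weekly patients receive more drug between checks, or that the protocol means to dose them without bloods. The documents support neither. The amounts are equal, and the blank looks like a six-weekly schedule not adapted to an option.

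**Conclusion.** The gap is real on a literal reading. For a patient kept on 3-weekly pembrolizumab after Cycle 9, every second infusion from C10 has no scheduled chemistry or CBC, and the latest scheduled values are 21 days old (15 to 27 with windows, if bloods are drawn on the even-cycle dosing day). The consequence is one missed scheduled chance per six weeks to withhold 200 mg for a silent, drug-related liver or renal rise.

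The size is modest. The default regimen is unaffected, and its interval between scheduled labs is the same 42 days. The protocol does not say how many patients will stay on 3-weekly dosing; it may be few or none. Nothing here bears on the co-primary endpoints or their analysis. This is a cheap improvement on a minor patient-safety point.

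**What to change.** Three wording changes:

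1. **Table 9.** Add X** for CBC and for chemistry in the odd-cycle column, with a footnote that they are required before any pembrolizumab infusion given at that cycle.
2. **Footnote **.** Limit the sentence on attendance only if clinically indicated to odd cycles without a pembrolizumab infusion.
3. **Section 10.1.** State that six-weekly monitoring after Cycle 9 applies unless pembrolizumab is being given every 3 weeks or closer monitoring is clinically indicated.

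No separate rule is needed for patients who switch early to 400 mg every 6 weeks. If such a patient starts 400 mg at the C7 imaging visit and keeps a six-week rhythm, doses fall on C9, C11 and C13, and the infusion-linked footnote covers them. Forcing these patients onto even cycles would add a visit for those the option is meant to spare travel.

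The cost is an amendment of a few lines and routine bloods at infusion visits already attended. Patients on the default regimen see no change.

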Wilcoxon rank sum test will be used to assess associations between genetic and transcriptomic signatures at baseline with response while Cox regression will be used to assess associations with PFS and OS. These analyses will be conducted separately for each cohort acknowledging the exploratory nature of these analyses particularly for Cohorts B and C which have limited sample size. Changes between baseline and after treatment in neoantigen induction, TME, and immunomodulatory targets will be summarized descriptively using medians and interquartile range for each cohort separately. To understand the resistance mechanisms, post-treatment changes (4-6 weeks and at progression) of tumor samples and circulating tumor DNA (MSK-ACCESS) from baseline will be associated with response using Wilcoxon rank sum test while Cox regression will be used for PFS and OS outcomes. Finally, in selected patients with viable organoids available from IRB# 15-149 prior to enrollment to POLAR trial, we will concurrently evaluate the response of organoid to POLAR in real time as participants are treated in parallel. Dr. [name] will oversee this part. PFS2 will be estimated using the Kaplan-Meier method. Associations between genetic mutations (HRD and non-HRD) and outcome will be assessed using Fisher's exact test for response and log-rank test for survival outcomes. Biomarkers (reversion mutation, zygosity, plasticity, aneuploidy from tumor, and circulating tumor DNA) will be summarized using proportions. Presence of circulating tumor DNA and levels of CA 19-9 prior to treatment at time points prior to consent and between the consent and start date will be graphically summarized at each timepoint.

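### The end-of-treatment blood and cfDNA draw is not tied to the start of the next anticancer therapy, and Table 9 footnote 3 omits the limit that Section 4.2 sets for tissue

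*Protocol*

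**What the plan says.** **Tissue.** Section 4.2 (Research Tissue Collection) sets the timing of the progression sample: "post-progression (before initiation of further therapy) will be obtained where feasible". It also makes the procedure obligatory, with an exception for safety or lack of an accessible site: "Biopsies are mandated by protocol baseline and on treatment and at the time of progression except". Table 9 footnote 3 (Section 11.1) gives a window around end of treatment: "Every effort should be made to obtain EOT (+/- 28 days) biopsies in cases of RECIST v1.1 confirmed disease progression". This applies "if a patient discontinues study treatment due to disease progression". The footnote says nothing about the next therapy.

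**Blood.** Footnote 4 lists six immune-profiling draws, the last being number "6 with EOT (+/-21 days". Footnote 5 covers cfDNA by reference to the same numbered draws: "TOPCOAT-POLAR will handle for MSK ACCESS #1-#6 time points for All Cohorts". It states no window of its own, so the 21 days for cfDNA is an inference from footnote 4.

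**Use of the samples.** Section 14.0, under the exploratory objectives, describes the resistance analysis: "post-treatment changes (4-6 weeks and at progression) of tumor samples and circulating tumor DNA (MSK-ACCESS) from baseline will be associated with response". Cox regression is planned for PFS and OS.

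**The concern.** The at-progression sample is meant to show what the tumor and circulating DNA look like after POLAR has stopped working. Once another anticancer drug has been given, changes in ctDNA level, clonal make-up or immune cells can no longer be attributed to POLAR alone. They may mask resistance to POLAR or resemble it. Patients who need new treatment soonest after stopping are the ones most likely to be sampled late relative to it, so any such error could be related to outcome. Section 3.3 names translational science as the focus of the trial alongside clinical activity. The cohorts are small (33, 15 and 15 at most), so a handful of mistimed samples could matter to these analyses.

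**Working it through.** The plan states no figure to reproduce. The check sets the passages side by side and then does simple window arithmetic.

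**Step 1: is there a limit at the next therapy?**
- Tissue: yes in Section 4.2, qualified by feasibility; absent from footnote 3.
- Immune-profiling blood: none in footnote 4, in Section 4.2 (Research Blood Collection) or elsewhere in the text shown.
- cfDNA: none in footnote 5 or elsewhere in the text shown.

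**Step 2: can the next therapy start inside the window?** The protocol gives no minimum interval from end of treatment to new therapy. Section 15.0 foresees new anticancer therapy during follow-up, because it shortens the serious adverse event reporting period when that happens. So it can.

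**Step 3: how much of the permitted window could fall after the next therapy starts?** Let W be the days allowed after end of treatment (28 for biopsy, 21 for blood). Let d be the days from end of treatment to the next therapy. The documents do not give d; 7 to 28 days is assumed here. The share of permitted post-treatment days that fall after the start of next therapy is max(0, W − d) / W.
- d = 7: biopsy 21/28 = 75%; blood 14/21 = 67%
- d = 14: biopsy 14/28 = 50%; blood 7/21 = 33%
- d = 21: biopsy 7/28 = 25%; blood 0/21 = 0%
- d = 28: both 0%

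These are shares of permitted days, not of samples. The biopsy figures describe footnote 3 read alone. With Section 4.2 applied as well, the share for tissue is 0 wherever a biopsy before further therapy is feasible.

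**Step 4: after the change.** If the window closes at the first dose of subsequent therapy, the share is 0 for every d. No sample size, power or alpha figure changes.

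**The case against.** The strongest case against has four parts.

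*Tissue is already covered.* A biopsy can be both within 28 days of end of treatment and before further therapy, and nothing says that Table 9 overrides Section 4.2. This stands. A reader might infer that the schedule replaces the Section 4.2 rule, but the text shows only an omission.

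*The early half of the window is harmless.* A reader might infer that, for a patient who stops at the week-9 scan, one specimen could serve as both the on-treatment and the progression sample, because 28 days before end of treatment reaches back to week 5. The documents do not support this. Footnote 3 applies to confirmed progression, footnote 2 describes a separate repeat biopsy, and no passage lets one specimen fill both slots. The early half also has a natural purpose: Sections 10.1 and 12.1 allow treatment beyond RECIST progression, so a progression biopsy can precede end of treatment.

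*The percentages are not contamination rates.* Table 9 schedules these samples at the time of discontinuation, and the plus-or-minus days are a tolerance, so sampling need not be even across the window. The two-week interval in exclusion criterion 13 is a washout before POLAR and says nothing about the gap after it. Both points stand.

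*Other text may settle the matter.* Section 4.2 refers to the Biomarker Management Plan (Appendix 3) for time points, and its content is not shown. It may restrict timing. Leaving out late samples is also an analysis rule that a statistical analysis plan might carry. This lowers the weight of the point but does not remove it: the protocol's own blood window is stated without the limit, and footnote 3 should agree with Section 4.2 in any case.

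**Conclusion.** The point holds for blood and, by inference, for cfDNA. On the text shown, a draw taken after the next therapy has begun but within 21 days of end of treatment is fully compliant, and it would enter an analysis meant to describe resistance to POLAR. For tissue the defect is smaller: footnote 3 omits a limit that Section 4.2 sets, so staff working from Table 9 alone could biopsy late, and the two passages need reconciling.

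The size is unknown. The documents give neither the interval to the next therapy nor the actual sampling days, so the number of affected samples cannot be derived; the shares above only show where overlap becomes possible. The conclusion rests on cfDNA sharing the footnote 4 window and on the Biomarker Management Plan not already closing the gap. The consequence is confined to exploratory resistance analyses. The co-primary endpoints, sample size, power and type I error are unaffected. It is a modest but worthwhile clarification.

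**What to change.** In footnotes 3, 4 and 5 of Table 9, add to the end-of-treatment time point: *and before the first dose of any subsequent anticancer therapy*. State the window for cfDNA explicitly in footnote 5. Samples taken after that date are banked and either left out of, or flagged in, the at-progression change analysis.

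Do not make the blood draws conditional on a date of RECIST progression. The end-of-treatment draws also apply to patients who stop for toxicity or other reasons, and such a condition would remove their time point.

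The cost is one clause in three footnotes and one date comparison in the analysis. PFS2 (Sections 2.0 and 14.0) already needs the start date of subsequent systemic treatment. The reporting rule in Section 15.0 already requires knowing whether new anticancer therapy of any kind has begun. The downside is that a few end-of-treatment samples drop out of the analysis when new therapy starts quickly. The Biomarker Management Plan should be checked so that it carries the same limit.
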